### 9.5.1 Primary Outcomes

The primary objectives of this study are to determine the efficacy of antiseptic mouthwashes on reducing SARS-CoV-2 viral RNA and protein antigen levels in COVID+ patient saliva. *We hypothesize that COVID-19+ patients will have a >95% reduction in SARS-CoV-2 viral RNA and protein antigen levels following a 60 second oral rinse with an antiseptic mouthrinse and that this reduction will persist for at least 30 minutes.* These primary objectives will assess SARS-CoV-2 viral load based on viral RNA measured by quantitative real time PCR and viral protein antigen levels measured by rapid antigen or sandwich ELISA assays. These objectives provides urgently needed data to guide healthcare workers on the proper use of specific commercially available

mouthwashes capable of reducing SARS-CoV-2 in saliva and potentially limiting COVID-19+ transmission.

Outcome assessments will be conducted weeks to months after the study visit, when qRT-PCR and sandwich ELISA or rapid antigen assays are conducted in the COVID core and the [name] lab.

### 9.5.2 Tertiary Outcomes

The first tertiary objective will focus on quantifying SARS-CoV-2 viral infectivity using an *in vitro* infectivity assay. *We hypothesize that COVID-19+ patients will have a >95% reduction in SARS-CoV-2 viral infectivity following a 60 second oral rinse with an antiseptic mouthrinse and that this reduction will persist for at least 30 minutes.* This objective provides urgently needed data to guide healthcare workers on the proper use of specific commercially available mouthwashes capable of reducing SARS-CoV-2 viral infectivity and potentially limiting COVID-19+ transmission. Our second tertiary objective is to determine the **feasibility** and **acceptability** of using antiseptic mouthwashes by patients in healthcare settings. *We hypothesize that patients will welcome the use of commercially available antiseptic mouthrinses into clinical practice.* Patients enrolled in the randomized mouthrinse study will be surveyed on the taste, appearance, sensation, and acceptability of using the mouthrinse in healthcare settings. Understanding acceptability of a mouthrinse protocol is critical to implementation and therefore the ability to reduce COVID-19 transmission risk in clinical settings.

Outcome assessments will be conducted weeks to months after the study visit, when viral infectivity assays are conducted in the COVID core and the [name] lab.

Survey results will be evaluated using bivariate, descriptive statistics and non-parametric methods as appropriate for the question type. Outcome assessments will be conducted weeks to months after the study visit, when statistical analyses are conducted.

## 9.6 Data Analyses

qRT-PCR and sandwich ELISA or rapid antigen: Data will be presented as mean standard deviation for normally distributed data and as median [Interquartile range] for non-normally distributed data. P values will be reported as two tailed. Between group comparisons will be performed using a Students t test or Mann-Whitney test. Normality will be assessed using the Kolmogorov-Smirnov test, and logistic regression will be performed with robust standard errors. Methods adapted from Bullard *et al* 2020.

Viral infectivity: The viral infectivity analysis will compare infectivity levels between mouth rinse types and across the time course for calculation of the reduction factor (RF). The RF will be calculated as the difference in the quotient of the infection titre before ('control titration') and after

the mouthrinse ('remaining virus'). Therefore, the log10 titre and its (double) standard deviation (SD) were calculated as well as the variance of the RF.

Survey results will be evaluated using bivariate, descriptive statistics and non-parametric methods as appropriate for the question type.

Power Calculation: Based on similar viral infectivity studies evaluating mouth rinse efficacy against other enveloped viruses, we used power calculations to estimate effect size and determine sample size as a function of length of mouthrinse time course. The sample size is justified by a paired t-test on outcomes between time points. With ten simultaneous comparisons (T1-T0, T2-T1, T2-T0, T3-T0, T3-T2, T3-T1, T4-T3, T4-T2, T4-T1, T4-T0) = 60 minute time course, the sample size n=78 can detect the effect size in Cohen's d =0.7, which is between medium and large, under 80% power and 0.016 type-I error rate by Bonferroni correction. Analyses will compare viral RNA level (qRT-PCR), protein level (sandwich ELISA and rapid antigen) or viral infectivity levels between mouth rinse types and across the time course. ANCOVA models will be utilized to look at changes in viral load and infectivity logarithmically before and after treatment.

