## 5. STUDY INTERVENTIONS

### 5.1 Interventions, Administration, and Duration

Patients who meet all inclusion criteria without any exclusions will be asked to give a baseline salivary sample of 5ml over 10 minutes. The patient will then be asked to rinse with an unlabeled/blinded antiseptic mouth rinse for 60 seconds. Once s/he expectorates the mouth rinse, a time 0, 2ml salivary sample will be collected over 5 minutes. Then the patient will have 10 minutes to recuperate, while answering survey questions about their demographics and regarding the taste, color, flavor and acceptability of using the mouth rinse as part of routine dental and medical visits. Patients will be asked to smell an ammonia ampule ('smelling salt') to evaluate sense of smell, as loss of olfaction is indicative of the acute infection phase. At 15 minutes post-rinse, the patient will be asked to provide an additional 2ml saliva samples over 5 minutes, followed by another 10 minute break. This sequence repeats for the 30, 45 and 60 minute time points. At 60 minutes, the patient will give their last 2ml salivary sample, and study participation will conclude. Participants will be provided with a gift card for their participation.

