#### **Primary Outcomes**

The analyses will compare viral RNA level (qRT-PCR) and protein antigen level (sandwich ELISA or rapid antigen) of SARS-CoV-2 between mouth rinse types and across the time course.

Data generated from the qRT-PCR and sandwich ELISA or rapid antigen assays will be presented as mean standard deviation for normally distributed data and as median [Interquartile range] for

non-normally distributed data. P values will be reported as two tailed. Between group comparisons will be performed using a Student's t test or Mann-Whitney U test. Normality will be assessed using the Kolmogorov-Smirnov test, and logistic regression will be performed with robust standard errors.

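### For the primary RNA and antigen outcomes several methods are named and none is ranked; the stated between-arm test does not use the pre-rinse sample, and the baseline-adjusted log10 ANCOVA should be made primary

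*Combined protocol and SAP*

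**What the plan says.** Section 9.1, under Primary Outcomes, sets the quantity to be compared: "The analyses will compare viral RNA level (qRT-PCR) and protein antigen level (sandwich ELISA or rapid antigen) of SARS-CoV-2 between mouth rinse types", and also over time. Section 9.6 gives the test: "Between group comparisons will be performed using a Students t test or Mann-Whitney test". Neither place names a covariate, a change score, a time point or a scale (raw or log10) for that test.

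Both places then bring in a normality test; 9.1 has "Normality will be assessed using the Kolmogorov-Smirnov test", and 9.6 has "Normality will be assessed using the Kolmogorov-Smirnov test, and logistic regression will be performed with robust standard errors". Both also list a logistic regression with robust standard errors, without saying what its dependent variable is.

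A further method appears once, at the end of the power paragraph in 9.6: "ANCOVA models will be utilized to look at changes in viral load and infectivity logarithmically before and after treatment". The Primary Outcomes text in 9.1 does not mention it.

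The sample size rests on yet another method: "The sample size is justified by a paired t-test on outcomes between time points".

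A pre-rinse measurement is available. Under 5.1 each participant is "asked to give a baseline salivary sample of 5ml over 10 minutes". After the rinse, "a time 0, 2ml salivary sample will be collected over 5 minutes". Time 0 is therefore a post-rinse sample, and none of the ten contrasts listed for the sample size (all among T0 to T4) involves the pre-rinse sample. The primary hypothesis in 9.5.1 is a reduction of more than 95% following the rinse and lasting at least 30 minutes, which is naturally a change from pre-rinse.

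**The concern.** No section says which analysis is primary. Two things are at stake.

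- **Precision.** The between-arm test that the plan names for the primary outcomes compares post-rinse levels without adjustment. Salivary viral load before the rinse will differ between participants. If it predicts the post-rinse value, leaving it out adds avoidable variance, although the sample is already collected. A comparison of levels also does not estimate the reduction that the hypothesis is about, and a Mann-Whitney p-value gives no percentage at all.
- **Choice after the data are seen.** The t test, Mann-Whitney test, ANCOVA and logistic regression stand side by side, with the scale open and the quantity described as a level in one sentence and a change in another. Different choices can give different answers. Section 9.5 says the committee that draws the conclusions is not masked to group assignment, so a fixed primary analysis matters more here.

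**Working it through.** **Inputs from the documents.** 80 per arm, six arms (Précis and Section 3); two-tailed p-values (9.6); a pre-rinse sample from every participant (5.1).

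**Assumptions, not in the documents.** The correlation ρ between pre-rinse and post-rinse log10 values; equal variance before and after the rinse; a true between-arm difference of 0.4 SD; two-sided 5% for a single contrast.

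**The plan's own figure.** The only figure is n=78 for a within-arm paired t test. A two-sided paired t test with d=0.7, alpha 0.016 and 80% power needs 25, so 78 is not reproduced. That is a separate matter. Nothing below depends on it, and the plan gives no power figure for any between-arm test.

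**Step 1: precision.** With the variance of a post-rinse level set to 1, the relative variance v is:
- level only: 1
- change score: 2(1−ρ)
- ANCOVA on the pre-rinse value: 1−ρ²

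Equivalent sample size per arm = 80/v. Detectable difference at 80% power = (1.96+0.842)·√(2v/80) SD. Power = Φ(0.4/√(2v/80) − 1.96).

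| Analysis | ρ | v | 80 per arm acts like | Detectable difference (SD) | Power for 0.4 SD |
|---|---|---|---|---|---|
| Level t test | any | 1 | 80 | 0.44 | 71.6% |
| ANCOVA | 0.3 | 1−0.09 = 0.91 | 88 | 0.42 | 75.6% |
| ANCOVA | 0.5 | 1−0.25 = 0.75 | 107 | 0.38 | 83.2% |
| ANCOVA | 0.7 | 1−0.49 = 0.51 | 157 | 0.32 | 94.3% |

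For example, with the level test 0.4/√(2/80) = 2.530, and Φ(2.530−1.96) = 0.716.

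If the t test were instead run on change scores, the ratio of ANCOVA variance to change-score variance is (1−ρ²)/(2(1−ρ)) = (1+ρ)/2. That is 0.65, 0.75 and 0.85 at ρ = 0.3, 0.5 and 0.7. Against that comparator, 80 per arm at ρ=0.7 acts like 80/0.85 = 94, not 157. At ρ=0.3 the change score is worse than the level test (v = 1.40).

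**Step 2: unranked methods.** Null data were simulated for one contrast, one outcome and one time point (80 per arm, normal log10 values, 6,000 trials per setting). Each of level t, Mann-Whitney, change-score t and ANCOVA rejected close to 5% alone (4.4–5.1%). At least one of the four gave p<0.05 in 9.7%, 10.3%, 10.6% and 11.1% of trials at ρ = 0.3, 0.5, 0.7 and 0.9.

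**Step 3: what the normality test does.** At n=80, with mean and SD estimated from the sample, the Kolmogorov-Smirnov test rejected 0% of normal log10 samples and 100% of raw-copy samples (assumed log10 SD 1). When 10%, 20% or 30% of log10 values sit at a detection limit, it rejected about 0%, 15% and 86%.

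- Raw copies (assumed log10 SD 1.5, shift 0.7 SD): t power 18%, Mann-Whitney 99%; the two disagree in 81% of trials.
- Log10 values, 30% at the limit, shift 0.4 SD: 63% and 66%; they disagree in 12%.
- Using the normality test as a fixed rule to choose the test kept null rejection at 4.95–5.4%.

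So the unstated scale matters far more than the pretest itself.

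**The case against.** The strongest reply is that 9.6 does plan a baseline-aware analysis. The ANCOVA sentence speaks of log-scale change from before to after treatment, and it directly follows a sentence on comparing rinses over the time course. On that reading ANCOVA is the main model and the t and Mann-Whitney tests are supporting summaries. This stands in part: a reader might infer that the plan as a whole ignores the pre-rinse value, and it does not. But 9.1 leaves ANCOVA out, and 9.6 gives it no covariate, contrast, time point or rank, so the favourable reading has to be supplied by the reader.

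Other stronger readings also fail:

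- *The primary test is chosen by a Kolmogorov-Smirnov rule.* This is inferred from adjacent sentences. The explicit distinction between normal and non-normal data governs only how data are presented (mean with SD, or median with IQR).
- *The pretest inflates type I error.* The simulations did not show this.
- *The test could switch between interim and final.* The interim rule in 9.4 concerns infectivity. The normality test is listed only for RNA and antigen, and no interim test of those outcomes is described.
- *Logistic regression is impossible because every outcome is continuous.* The Précis and 9.1 speak of detection and detectable RNA, and 9.5.1 gives a 95% threshold. The fault is that the outcome is undefined.

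It is also fair that the precision gain is modest at ρ=0.3, that ρ is unknown, and that a change-score t test is not named in the plan. Without it, the best-of-several error rate in Step 2 would be lower. Section 9.6 says its methods are adapted from a published study, which was not available here.

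**Conclusion.** The point holds as a gap in specification with a nearly free improvement. The named between-arm test for the primary outcomes is unadjusted and on an unstated scale; the ANCOVA has no assigned role; the logistic regression has no outcome.

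Against a level-only test, baseline adjustment makes 80 per arm act like 88 to 157 over assumed correlations of 0.3 to 0.7. Above a correlation of 0.5 the gain is smaller if change scores would otherwise have been analysed. Unrestricted choice among four plausible tests roughly doubles the nominal 5% for a single contrast, to about 10–11%. That is the cost of choosing the most favourable result, not evidence that anyone would. The switching figures for the normality test depend heavily on the assumed share of values at the detection limit and should not carry the argument.

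This should be changed before analysis. The defect is the missing hierarchy and definitions, and confidence in that is high. The size of the precision loss is conditional on the correlation.

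**What to change.** In 9.1 (Primary Outcomes) and 9.6, use the same wording:

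1. Name the ANCOVA already mentioned as the primary analysis: a linear or repeated-measures model of log10 RNA, and likewise of log10 antigen, adjusted for the pre-rinse log10 value.
2. State the contrasts (each active rinse versus saline) and one primary time point consistent with the 30-minute hypothesis.
3. State how values below the detection limit are handled.
4. Report the within-arm percentage reduction from pre-rinse with a confidence interval. The contrast with saline alone does not estimate the reduction of more than 95% in the hypothesis.
5. Choose no test by a normality pretest. Keep Mann-Whitney as a sensitivity analysis.
6. Either define a binary outcome for the logistic regression (for example, more than 95% reduction, yes or no) or delete it.

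The multiplicity rule for the five contrasts and two outcomes is a separate matter that this wording does not settle.

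The cost is wording only. The pre-rinse sample is already collected and ANCOVA is already in 9.6; no visit, assay or participant is added.

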## 1. STUDY OBJECTIVES

### 1.1 Primary Objectives

The primary objectives of this study are to determine the efficacy of antiseptic mouthwashes on reducing SARS-CoV-2 viral RNA and protein antigen levels in COVID+ patient saliva. *We hypothesize that COVID-19+ patients will have a >95% reduction in SARS-CoV-2 viral RNA and protein antigen levels following a 60 second oral rinse with an antiseptic mouthrinse and that this reduction will persist for at least 30 minutes.* These primary objectives will assess SARS-CoV-2 viral load based on viral RNA measured by quantitative real time PCR and viral protein antigen levels measured by rapid antigen or sandwich ELISA assays. These objectives provides urgently needed data to guide healthcare workers on the proper use of specific commercially available mouthwashes capable of reducing SARS-CoV-2 in saliva and potentially limiting COVID-19+ transmission.

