After the participant expectorates the mouth rinse, research staff will collect another salivary sample (T0, 2 mL over 5 minutes). During a 10 minute recuperation period, the study participants will answer demographics survey questions and questions regarding the taste, color, flavor and general acceptability of using the mouthrinse as part of routine dental and medical visits. Patients will be asked to smell an ammonia ampule (“smelling salts”) to evaluate sense of smell, as loss of olfaction is indicative of the acute infection phase. At 15 minutes post-rinse, the participant will be asked to provide an additional saliva sample (2 mL over 5 minutes), followed by another 10 minute recuperation period. This sequence will be repeated for at the 30, 45 and 60 minute time points post rinse. At 60 minutes, the study participant will give their final salivary sample (2 mL over 5 min), and study participation will conclude.

All salivary samples will be collected on ice in sterile 15 mL conical vials labelled “COVID Core” and using pre-printed labels including patient’s random alphanumeric study ID. Saliva samples will be cataloged and stored at the UNC Delta COVID Translational Initiative (also known as the Covid-19 Core) for future qRT-PCR, viral infectivity, and rapid antigen or sandwich ELISA assays. Samples will be transported on ice from the collection site to 4403A Koury Hall in leak proof biohazard bags. Samples will be processed according to the **sample processing and outcomes** procedure (below).

Following study participation completion, participants will receive \$50 compensation in the form of a Visa gift card.

During the period that the COVID+ study participants are present in the clinic and giving saliva samples, we will monitor oxygen saturation and inquire about their comfort. If participants exhibit signs of distress or if oxygen saturation drops, research study staff will contact emergency medical responders (present in the building) to visit the patient and if deemed appropriate, the participants will be escorted to UNC hospital (adjacent building).

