#### **Sample Size Considerations**

Based on similar viral infectivity studies evaluating antiviral mouth rinse efficacy, we were able to run power calculations to estimate effect size and determine sample size as a function of length of mouthrinse time course. The sample size is justified by a paired t-test on outcomes between time points. With three simultaneous comparisons (T1-T0, T2-T1, and T2-T0 = 30 minute time course), the sample size n=6 can detect the effect size in Cohen's  $d=0.7$ , which is between medium and large, over 80% power and 0.016 type-I error rate by Bonferroni correction. With six simultaneous comparisons (T1-T0, T2-T1, T2-T0, T3-T0, T3-T2, T3-T1) = 45 minute time course, the sample size n=53 can detect the effect size in Cohen's  $d=0.7$ , which is between medium and large, over 80% power and 0.016 type-I error rate by Bonferroni correction. With ten simultaneous comparisons (T1-T0, T2-T1, T2-T0, T3-T0, T3-T2, T3-T1, T4-T3, T4-T2, T4-T1, T4-T0) = 60 minute time course, the sample size n=78 can detect the effect size in Cohen's  $d=0.7$ , which is between medium and large, over 80% power and 0.016 type-I error rate by Bonferroni correction.

Statistical analysis of our data will be performed by [name], the statistician on this project.

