## **9.2 Sample Size and Randomization**

Based on similar viral infectivity studies evaluating antiviral mouth rinse efficacy, we were able to run power calculations to estimate effect size and determine sample size as a function of length of mouthrinse time course. The sample size is justified by a paired t-test on outcomes between time points. With three simultaneous comparisons (T1-T0, T2-T1, and T2-T0 = 30 minute time course), the sample size n=6 can detect the effect size in Cohen's d =0.7, which is between medium and large, under 80% power and 0.016 type-I error rate by Bonferroni correction. With six simultaneous comparisons (T1-T0, T2-T1, T2-T0, T3-T0, T3-T2, T3-T1) = 45 minute time course, the sample size n=53 can detect the effect size in Cohen's d =0.7, which is between medium and large, under 80% power and 0.016 type-I error rate by Bonferroni correction. With ten simultaneous comparisons (T1-T0, T2-T1, T2-T0, T3-T0, T3-T2, T3-T1, T4-T3, T4-T2, T4-T1, T4-T0) = 60 minute time course, the sample size n=78 can detect the effect size in Cohen's d =0.7, which is between medium and large, under 80% power and 0.016 type-I error rate by Bonferroni correction.

[name], who is the statistical consultant on this project, will create a block randomization schedule and perform these computations. All patients will be consented and then fill out our screening questions for inclusion and exclusion to confirm eligibility prior to being assigned to the randomization schedule.

The researcher responsible for collecting the salivary samples will be blinded to the mouthwash solution, as they will be given a pre-aliquoted mouthrinse in an unlabeled storage syringe to provide to the patient for the rinse. The syringe will be opaque to mask any coloring of the solution.

The PI, Co-I, study coordinators and study personnel who work for GoHealth are authorized to break the blinding if a patient suffers an allergic or adverse reaction to one of the mouthrinses. Though highly unlikely as all mouthrinses are sold commercially at Walgreens and CVS, adverse or allergic reactions are possible. Using the numerical code associated with the participant and mouthrinse syringe, the study personnel can reference the block randomization schedule to determine the mouthrinse type, to inform the emergency medical workers, poison control or the emergency room what type of mouthrinse product led to the reaction.

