## 9.5 Outcomes

All oral rinse products are commercially available, low risk products. Therefore, adverse outcomes are anticipated to be extremely rare, and will be reviewed weekly by the study team/committee. Any adverse event will be documented in our CDART database system.

The qRT-PCR assay for our primary outcome will be documented in an excel spreadsheet generated by the qRT-PCR assay quantification device, available weeks to months after sample collection when the experiments are conducted. If qRT-PCR proves unsuccessful, antigen-based assays will be used instead to quantify viral protein antigen level (Spike or N protein) using a sandwich ELISA or rapid antigen assays. These outcomes will be documented in excel spreadsheets generated by study personnel, available weeks to months after sample collection when the experiments are conducted. Samples will be run in large batches to limit batch effects.

The viral infectivity assay for our tertiary outcome will be documented in an excel spreadsheet generated by the viral infectivity assay quantification device, available weeks to months after sample collection when the experiments are conducted. Survey results will also yield excel spreadsheets of data, available shortly after data collection completion.

The outcomes do not include patient treatment response, and therefore the outcomes will not be reviewed and adjudicated by an outside committee. The study personnel will constitute their own committee that meets weekly, and they will review and evaluate the data once these experiments are conducted. The committee will not be masked to the participant's group assignment; the statistician will conduct analyses and then the committee will evaluate the data to reach scientific conclusions on which mouthrinse is more effective.

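### The only stated power and alpha belong to within-arm contrasts among post-rinse samples, which cannot show the hypothesised reduction; the analyses that could show it are listed without a chosen contrast, alpha or power

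*Combined protocol and SAP*

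**What the plan says.** **Hypothesis.** Sections 1.1 and 9.5.1 predict "a >95% reduction in SARS-CoV-2 viral RNA and protein antigen levels following a 60 second oral rinse" and "that this reduction will persist for at least 30 minutes". Section 3 calls the trial placebo-controlled and lists 0.9% NaCl, 80 participants, as the control arm.

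**Sampling.** A 5 mL sample is taken before the rinse. Section 3 continues: "After the participant expectorates the mouth rinse, research staff will collect another salivary sample (T 0 , 2 mL over 5 minutes". Section 5.1 agrees: "Once s/he expectorates the mouth rinse, a time 0, 2ml salivary sample will be collected over 5 minutes". Further samples follow at 15, 30, 45 and 60 minutes.

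**Power.** Section 9.2 states: "The sample size is justified by a paired t-test on outcomes between time points". Section 9.6 gives the contrasts: "With ten simultaneous comparisons (T1-T0, T2-T1, T2-T0, T3-T0, T3-T2, T3-T1, T4-T3, T4-T2, T4-T1, T4-T0) = 60 minute time course". Sections 2.2, 9.1, 9.2 and 9.6 all list the ten contrasts among T0 to T4, with n=78, d=0.7, 80% power and a type I error of 0.016 attributed to Bonferroni. The Sample Size Considerations in 9.1 fix the time scale: "With three simultaneous comparisons (T1-T0, T2-T1, and T2-T0 = 30 minute time course".

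**Analysis.** Under the Primary Outcomes heading, section 9.1 plans to compare RNA and antigen across rinse types and over time, by t test or Mann-Whitney test. Section 9.6 repeats those tests and adds ANCOVA on the log scale, before against after treatment.

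**The concern.** A confirmatory claim that a rinse lowers salivary virus needs two comparisons: with the pre-rinse sample, to show a fall, and with saline, to separate an antiseptic effect from rinsing the mouth with any liquid. The only contrasts that carry a power and an alpha contain neither.

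They can also mislead in both directions. A rinse that works fully and lastingly gives null results on all ten. Wash-out followed by recovery can give non-zero differences with no antiviral effect.

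The choice among t test, Mann-Whitney test and ANCOVA, the time point or points tested, the explicit contrast with saline and the alpha are left to be settled later. Section 9.5 says that the committee drawing the conclusions will not be masked to assignment, so those choices could be made with results and arms in view.

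**Working it through.** **1. The plan's own figure.** For a paired t-test with d=0.7, two-sided alpha 0.016 and 80% power, the normal approximation is n = ((z for alpha + z for power)/d)² = ((2.409 + 0.842)/0.7)² = 21.6, so 22; the noncentral t gives 25. At alpha 0.005 the figures are 28 and 32. The stated 78 is not reproduced. That is a separate point and adds no weight here.

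**2. Which samples the contrasts use.** Six samples are taken: one pre-rinse and five post-rinse (0, 15, 30, 45, 60 minutes). With T0 after expectoration and T2−T0 spanning 30 minutes, T0 to T4 are the five post-rinse samples. C(5,2) = 10 uses them up exactly; including the pre-rinse sample would give C(6,2) = 15. So 0 of 10 contrasts contain the pre-rinse sample. A paired test is within participant, so 0 of 10 involve saline.

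The power paragraphs do not themselves define T0. If it meant the pre-rinse sample there, 4 of 10 contrasts would contain it, five labels could not cover six samples, and saline would still be absent.

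**3. What they can detect.** Let the mean log10 level be μ before the rinse and μ − δ at every later time. Each contrast is then (μ − δ) − (μ − δ) = 0 for any δ, including δ = 0. As an illustration, a simulation assumed a between-subject SD of 1.3 log10, an error SD of 0.7 log10, a constant fall of 1.301 log10 and n=80. At least one of the ten contrasts rejected at 0.016 in 11.6% of runs, all false positives. Pre-rinse against 30 minutes, and change against saline, each rejected in 100%.

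**4. Alpha.** 10 × 0.016 = 0.16, and 0.05/10 = 0.005. The figure 0.016 is close to 0.05/3 = 0.0167, the level for three contrasts.

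**5. Power for the contrasts that matter.** The documents give no between-arm effect size or SD; their d=0.7 is tied to a paired test. Between-arm d is therefore an assumption. For a two-sided two-sample t-test with 80 per arm, df = 158 and noncentrality = d × √(80/2) = 6.32d. For the ANCOVA, d is in units of the residual SD after baseline adjustment.

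| d | 5 tests (0.01) | 10 tests (0.005) | 15 tests (0.0033) | 30 tests (0.00167) |
|---|---|---|---|---|
| 1.0 | >99.9% | >99.9% | >99.9% | 99.9% |
| 0.7 | 96.4% | 94.1% | 92.4% | 88.8% |
| 0.6 | 88.1% | 82.7% | 79.0% | 72.3% |
| 0.5 | 71.0% | 62.4% | 57.3% | 48.8% |

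The families are 5 rinses; 5 × 2 endpoints; 5 × 3 time points; and 5 × 3 × 2.

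The table is per test. If a rinse must succeed at all of 0, 15 and 30 minutes (0.01 each, equal d, assumed correlation 0 to 0.8), simulated power per rinse is about 90–93% at d=0.7, 68–80% at d=0.6 and 36–57% at d=0.5.

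**6. Linking d to the hypothesis.** A 95% reduction is log10(20) = 1.30 log10. If the whole of it were a difference from saline, d=1.0 corresponds to a residual SD of 1.30, d=0.7 to 1.30/0.7 = 1.86 and d=0.5 to 1.30/0.5 = 2.6. A fall under saline would shrink the difference, and so d.

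**The case against.** The strongest reply is that the paired contrasts only justify the sample size, and that the real analyses are stated elsewhere. Much of this stands. Between-rinse comparisons appear under Primary Outcomes in section 9.1, and an ANCOVA using levels before and after treatment is in 9.6. The hypothesis supplies a threshold and a duration, and section 3 names a control arm. A reader might infer that the plan has no analysis able to show the effect; the documents do not support that. What is missing is the step from these elements to a test: which method, which contrast with saline, at which times, at what alpha and with what power.

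It is also fair to say that T1−T0 and T2−T0 bear on persistence to 30 minutes, and that section 9.1 gives viral kinetics and rebound as aims. So it would be wrong to say that the ten contrasts have nothing to do with the primary hypothesis. They address one clause of it, and only in one direction: a significant rise argues against persistence, but a non-significant T2−T0 does not prove it.

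Finally, ANCOVA with a rule requiring success at 0, 15 and 30 minutes is one defensible choice among several. The need is for a choice to be fixed in advance, not for this one in particular.

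**Conclusion.** The point holds and should be settled before any unblinded analysis. None of the ten powered contrasts can show the initial reduction or separate it from saline wash-out, and no analysis that could do so has a designated contrast, alpha, multiplicity rule or power. The alpha quoted for the ten contrasts is also wrong for that family, by a factor of 0.016/0.005 = 3.2.

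This rests on T0 being the post-expectoration sample, as sections 3 and 5.1 say. If T0 meant the pre-rinse sample in the power paragraphs, the first part would weaken, but saline would still be absent and the alpha still wrong.

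A reader might infer that 80 per arm is too few. The documents do not support that. Power against saline runs from 48.8% to 99.9% or more across the values of d and the families tabulated, and nothing in the documents says where the true d lies. Adequacy cannot be read from the plan either way.

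Two neighbouring matters are separate: the n=78 that does not reproduce, and the conflict between antigen as a primary outcome alongside RNA (1.1, 9.5.1) and antigen as a fallback (section 9.5: "If qRT-PCR proves unsuccessful, antigen-based assays will be used instead to quantify viral protein antigen level"). The second matters here only because it changes the size of the alpha family.

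**What to change.** 1. Make the planned log10 ANCOVA the confirmatory analysis: post-rinse level on arm and pre-rinse level, each active rinse against saline, at named time points covering the 30-minute window (for example 0, 15 and 30 minutes).
2. State the success rule and match alpha to it. If every time point must succeed, use 0.05/5 = 0.01 per rinse; if each counts separately, 0.05/15 = 0.0033. Halve either figure if RNA and antigen are both primary. Say how the family is handled if arms are dropped at the interim analysis in section 9.4.
3. Define T0 in the power paragraphs and give the pre-rinse sample its own label.
4. A difference from saline does not by itself establish a reduction above 95%. Report the estimated reduction with its confidence interval against 1.30 log10, both within arm from pre-rinse and relative to saline.
5. Replace the power statement with one for this family and success rule, with between-arm d declared as an assumption and shown over a range that includes values above 0.7.
6. Keep the T0–T4 contrasts as rebound analyses, at 0.005 each if alpha-adjusted.

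The cost is protocol and SAP wording, plus a power statement that is conditional on an assumed d and may look less favourable than the present one. The pre-rinse samples, saline arm and ANCOVA are already in the plan, and no enrolment is added.
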